10.4 Other Endpoint Analyses

The approach to testing for group differences for each continuous outcome (e.g., quality of life and fatigue summary scales, length of stay after surgical resection, cost) will be to test for the group effect in an analysis of covariance model with adjustment for covariates listed in Section 10.1 as well as baseline values of the outcome variable when available.

Cost data and utilization data are typically positively skewed with some patients having very high costs/utilization. To reflect the distributions of cost and utilization, a generalized linear regression (GLM) with log link and gamma distribution and the generalized beta of the second kind (GB2) will be applied. To examine health care utilization, a Negative Binomial Regression (NBR) will be used to handle over dispersion of patient visits.

The proportion of patients who continue to smoke post-surgery is expected to be too small to include as a reliable adjustment variable or outcome ($\sim 5\%$).⁸⁹ Former smokers will be tested (saliva) at the 6 month clinic visit to assess smoking recidivism. A separate descriptive analysis will be performed in the subset of smokers.

An analogous approach will be used for endpoints coded as binary variables (complications, readmission) using logistic regression models instead of analysis of

covariance models. If diagnostics plots show significant deviation from model assumptions, then a separate sensitivity analysis will be performed using appropriate robust regression methods such as those available in the “robust base” package in R.

The study design provides 96% power to detect a 10 point increase in FACT-L in the Intervention Group compared to the Control Group, similar to the effect of aerobic training on FACT-L reported in Jones.⁴⁶

Bland-Altman analysis will be used to analyze agreement between remote and in clinic 6MW and for calculation of 95% confidence intervals on limits of agreement. The intra-class correlation coefficient will also be reported. Gaussian linear regression models will be used to determine whether remote 6MW and other covariates listed in Section 10 can be used to predict in clinic 6MW. Cross-validation will be used to evaluate performance.

Gaussian linear regression models will be used to assess the ability to predict 6MW from covariates listed in Section 10.1 and previous 6MW. Cross-validation will be used to assess the performance.

For estimation of mediation, mixed effects regression analysis will be performed with random slope and intercept for each participant and unstructured covariance matrix. The direct and indirect effects of the intervention will be examined. Indirect effects analysis can provide important information about underlying mechanisms (e.g., treatments could achieve the same outcome via different mechanisms). Particular attention will be paid to the potential mediating/moderating effects of pain and self-efficacy. For indirect effects analyses, sensitivity analyses will be conducted to examine the robustness of effects under different assumptions regarding missing data. Gender-specific effects of the intervention will also be investigated.

A limited dataset (including first name, email address, zip code and study ID number) for the COVID-19 questionnaires may be shared and analyzed with IRB_00140849 ‘Exemption Umbrella Protocol- HCI projects. This will facilitate a larger review of the impact of COVID-19 on all patient populations listed in the umbrella protocol.

11 REGISTRATION GUIDELINES

Patients must meet all of the eligibility requirements listed in Section 5 prior to registration.

Patients must not have any study procedures or begin protocol treatment prior to registration.

Randomization to the Intervention or Control Arm will be done at the time of enrollment by the enrolling coordinator using OnCore (the Clinical Trials Office’s electronic clinical research management system).

12 DATA SUBMISSION SCHEDULE

The Case Report Forms (CRFs) for this study are a set of electronic forms for each patient that provides a record of the data generated according to the protocol. CRFs should be created prior to the study being initiated and updated (if applicable) when amendments to the protocol are IRB approved. Data capture should be restricted to endpoints and relevant patient information required for planned manuscripts. These forms will be completed on an on-going basis during the study. The medical records will be source of verification of the data. During the study, the CRFs will be monitored for completeness, accuracy, legibility and attention to detail by a member of the Research Compliance Office. The CRFs will be completed by the Investigator or a member of the study team as listed on the Delegation of Duties Log. The data will be reviewed no less than annually by the Data and Safety Monitoring Committee. The Investigator will allow the Data and Safety Monitoring Committee or Research Compliance Office personnel access to the patient source documents, clinical supplies dispensing and storage area, and study documentation for the above-mentioned purpose. The Investigator further agrees to assist the site visitors in their activities.

13 SPECIAL INSTRUCTIONS

13.1 Correlative Studies – *Optional Participation*

13.1.1 Blood

Correlative blood samples will be taken at the pre-operative visit as well as at the 2 months post-surgery visit. A blood questionnaire will be completed during the time of blood collection, unless the participant declines the blood draw. Staff may ask the questions from the blood questionnaire remotely. The blood will not be collected if the Biospecimen and Molecular Pathology Shared Resource at the Huntsman Cancer Institute is closed at the time of collection.

One 10mL red top tube and two 10mL EDTA tube will be collected at each visit. Serum, plasma and buffy coat will be stored for future analysis.

13.1.2 Saliva

Patients will be asked to collect a saliva sample at 6 months follow-up. A saliva questionnaire will also be completed during the time of saliva collection, unless the participant declines providing the saliva. Staff may ask the questions from the saliva questionnaire remotely. The saliva will not be collected if the Biospecimen and Molecular Pathology Shared Resource at the Huntsman Cancer Institute is closed at the time of collection. Saliva samples will not be completed during the COVID-19 outbreak to ensure study personnel safety. The collection of saliva samples may resume if the study team decides the risk to study personnel safety is minimized.

13.1.3 Sample Sharing

Samples may be shared with internal studies including but not limited to the Total Cancer Study (IRB #89989). The samples shared with Total Cancer Care will be shared only if the participant has also signed the Total Cancer Care consent. Studies will need to submit a request as part of the standard Biospecimen Request Form” in writing to study principal investigators and specify the sample type, amount, purpose, and participant identifiers (if applicable) they are requesting. The principal investigators will either approve or disapprove of the request. All studies requesting samples will be outlined in the protocol.

14 ETHICAL AND REGULATORY CONSIDERATIONS

14.1 Informed Consent

Informed consent will be obtained from all research participants prior to performing any study procedures using the most recent IRB approved version.

14.2 Institutional Review

This study will be approved by the Institutional Review Board of University of Utah.

14.3 Data and Safety Monitoring Plan

A Data and Safety Monitoring Committee (DSMC) is established at Huntsman Cancer Institute (HCI) and approved by the NCI to assure the well-being of patients enrolled in Investigator Initiated Trials that do not have an outside monitoring review. Roles and responsibilities of the DSMC are set forth in the NCI approved plan. The activities of this committee include a quarterly review of adverse events including SAEs, important medical events, and significant revisions or amendments to the protocol. If the DSMC and/or the PI have concerns about unexpected safety issues, the study will be stopped and will not be resumed until the issues are resolved. The DSMC also reviews and approves audit reports generated by the Research Compliance Office.

14.4 Adverse Events / Serious Adverse Events

An adverse event is the appearance or worsening of any undesirable sign, symptom, or medical condition occurring after starting the study drug even if the event is not considered to be related to study drug. For the purposes of this study, the terms toxicity and adverse event are used interchangeably. Medical conditions/diseases present before starting study drug are only considered adverse events if they worsen after starting the PEP regimen. Abnormal test results constitute adverse events only if they induce clinical signs or symptoms, are considered clinically significant, or require therapy.

For this low-risk study, information about a subset of adverse events of interest will be collected, recorded and followed as appropriate. This subset includes **any injuries, events, and conditions with a causal relation to the PEP intervention and require medical attention.**

Study-Specific AE Reporting plan

There is no protocol-directed administration of systemic therapy in this nonpharmacologic study; patients may be taking standard of care anti-cancer therapy prescribed by their treating oncologist. This study poses no greater than minimal risk to the human subjects. Therefore, the study-specific AE reporting plan detailed below will be followed. Any AEs with a *causal* relation to the research will be reported as described below. Timing of reporting is based on the IRB standard reporting guidelines. The PI will determine the attribution/relatedness of each AE.

Reportable Events	Timing of Report to IRB
Unanticipated problem involving risks to subjects or others	Serious-within 7 days Non-Serious-with scheduled continuation
Any grade 3 or 4 physical, social, or psychological adverse events that are related or possibly related to participation in this research study (e.g., AE related to questionnaire completion, physical assessments) regardless of expectedness	Within 7 days
Death while on study related or possibly related to participation in this study	Within 7 days
Death while on study unrelated to participation in this study	With SCR
Non-Reportable Events 
 • Expected grade 1 or 2 side effects of exercise/activity, including typical muscle soreness associated with activity • Expected side effects of cancer therapy • Hospitalizations related to disease progression or scheduled surgeries • Any physical, social, or psychological harm grade 1 or 2 • Other serious events unrelated to participation in the research 	

Subjects will receive a systemic treatment regimen for their cancer during study participation. Since such routine interventions and treatment may influence the study results, information regarding the concomitant medications and toxicities experienced by each subject will be collected using the validated questionnaires but not reported to the IRB, as described above.

The occurrence of adverse events should be sought by non-directive questioning of the patient at each visit or phone contact during the study. Adverse events also may be detected when they are volunteered by the patient during or between visits or through physical examination or other assessments. As far as possible, each adverse event should be evaluated to determine:

1. Its severity grade based on CTCAE v.4 (grade 1-5).
2. Its relationship to the PEP intervention (definite, probable, possible, unlikely, not related).
3. Its duration (start and end dates or if continuing at final exam).
4. Action taken (no action taken; PEP intervention adjusted, temporarily interrupted, permanently discontinued due to this adverse event; concomitant medication taken; non-drug therapy given; hospitalization/prolonged hospitalization).
5. Whether it constitutes an SAE.

All adverse events will be treated appropriately. Such treatment may include changes in the intervention (as described in Figure 2). Once an adverse event is detected, it should be followed until its resolution, and assessment should be made at each visit (or more frequently, if necessary) of any changes in severity, the suspected relationship to the PEP regimen, the interventions required to treat it, and the outcome.

Study-Specific AE Reporting plan

There is no protocol-directed administration of systemic therapy in this nonpharmacologic study; patients may be taking standard of care anti-cancer therapy prescribed by their treating oncologist. This study poses no greater than minimal risk to the human subjects. Therefore, the study-specific AE reporting plan detailed below will be followed. Any AEs with a *causal* relation to the research will be reported as described below. Timing of reporting is based on the IRB standard reporting guidelines. The PI will determine the attribution/relatedness of each AE.

Reportable Events	Timing of Report to IRB
---------------------------------	---------------------------------------

Unanticipated problem involving risks to subjects or others	Serious-within 7 days
	Non-Serious-with scheduled continuation
Any grade 3 or 4 physical, social, or psychological adverse events that are related or possibly related to participation in this research study (e.g., AE related to questionnaire completion, physical assessments) regardless of expectedness	Within 7 days
Death while on study related or possibly related to participation in this study	Within 7 days
Death while on study unrelated to participation in this study	With SCR

Non-Reportable Events
 
  Expected grade 1 or 2 side effects of exercise/activity, including typical muscle soreness associated with activity  Expected side effects of cancer therapy  Hospitalizations related to disease progression or scheduled surgeries  Any physical, social, or psychological harm grade 1 or 2  Other serious events unrelated to participation in the research 	

Subjects will receive a systemic treatment regimen for their cancer during study participation. Since such routine interventions and treatment may influence the study results, information regarding the concomitant medications and toxicities experienced by each subject will be collected using the validated questionnaires but not reported to the IRB, as described above.

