3 STUDY DESIGN

3.1 Description

This is a Phase 3 study aimed at investigating the effects of a personalized exercise program (PEP) in NSCLC patients (stage I, II, IIIa) and secondary lung cancer patients undergoing surgical treatment at the University of Utah and comparing the intervention to the current standard of care (no exercise program).

Eligible patients will be randomized between two arms (1:1 ratio) prior to the surgery and will be followed for approximately 6 months post-surgery:

- An Intervention Arm (referred to in materials as Group 1), which features pre- and post-surgery PEP interventions.
- A Control Arm (referred to in materials as Group 2), which does not include a personalized exercise program (the standard of care). Patients randomized to Group

2 will be given the opportunity to participate in a PEP-intervention session providing exercise counseling after the 6 month assessment and will receive a free activity tracker for their participation.

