8.6 During the Follow-Up (Outpatient)

For patients randomized to Group 1, weekly telephone calls or TeleHealth interactions between the participant and the study team will continue as described in section 8.2.

8.7 Follow-Up Clinic Visits (2 and 6 Months Post-Surgery).

These visits are directly aligned with the patient's clinic visits and is contingent on clinic and patient availability. During times of unforeseen external impact, the 2 month visit may occur up to 4 months post-discharge and the 6 month visit may be completed up to one year post-discharge depending on the health of the patient and surgical policies. This window may increase if patient and surgical policies require it. The 6 month questionnaire may be completed on the date of the visit up to one year after the visit. The following procedures will be completed at the follow-up visits scheduled approximately 2 and 6 months after surgery:

- Assessment by physical therapist including AM-PAC mobility score (outpatient form). Staff may administer the AM-PAC with the participant remotely if the form cannot be given in clinic.

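### Section 14.4 gives two incompatible rules for which adverse events are recorded, and falls, injuries and other non-serious events have no equal capture or table by arm

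*Combined protocol and SAP*

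**What the plan says.** Section 14.4 opens with a cause-neutral definition: an event counts even if it is not thought related to the study drug. It then narrows what is kept. For what it calls a low-risk study, "information about a subset of adverse events of interest will be collected, recorded and followed as appropriate", and that subset is described as injuries, events and conditions "with a causal relation to the PEP intervention and require medical attention". The investigator decides relatedness.

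Onset is tied to treatment: "Medical conditions/diseases present before starting study drug are only considered adverse events if they worsen after starting the PEP regimen". The trial has no drug. Group 2 receives no PEP during comparative follow-up; Section 3.1 offers it a session "providing exercise counseling after the 6 month assessment", and Section 5.1 agrees.

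Later in Section 14.4 the instruction is wider: "The occurrence of adverse events should be sought by non-directive questioning of the patient at each visit or phone contact during the study". Each event is then to be assessed for "Its relationship to the PEP intervention (definite, probable, possible, unlikely, not related").

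Contact differs by arm. Section 8.6 reads "For patients randomized to Group 1, weekly telephone calls or TeleHealth interactions", continuing the pre-surgery calls of Section 8.2; the schedule in Section 6 marks these calls as applying only to patients in the PEP intervention. Both arms attend the discharge, 2-month and 6-month visits.

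Section 10 specifies no adverse event tabulation or analysis by arm. It does cover complications, readmission, cost and utilization (Section 10.4).

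**The concern.** A restriction on what is sent to the IRB would be routine in a low-risk behavioural trial. This one is worded as a restriction on what is collected and recorded. A rule that asks whether PEP caused the event before the event enters the database gives a count that depends on attribution, made by staff who are not described as masked, and that can only come from one arm. A patient in Group 1 who falls on a walk may be recorded; a patient in Group 2 who falls on a walk is not. If a fall in Group 1 is judged unrelated, the rule does not require it to be kept either.

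At stake is the safety statement of a Phase 3 trial of largely home-based exercise around lung resection. If site staff follow different halves of Section 14.4, the data will be inconsistent as well as asymmetric, and the trial could support neither a claim that home exercise is safe nor a claim that it is not, for the minor and moderate events most plausibly linked to exercise.

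**Working it through.** The documents give no adverse event rate, safety power or safety sample size, so there is no figure to reproduce. The check is a reading of the passages together, followed by an illustration of scale.

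**1. The two rules.**
- Narrow rule: only PEP-caused events needing medical attention are recorded. The lower relatedness grades would then have nothing to describe, and Group 2 can have no entry before the 6-month assessment.
- Wide rule: any event is sought from any patient at any contact and graded for relatedness afterwards. The scale makes sense only under this rule.

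**2. Ascertainment under the wide rule.** Both arms have three post-surgery visits, and both have the activity-recall contacts. Group 1 adds weekly calls before and after surgery. Sections 5.2.2 and 8.2 allow these to be delayed, missed or made less often, so one call per week is a ceiling.

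**3. What other both-arm routes cover.**
- Serious adverse events: Section 14.5 sends them to the safety committee with no limit by arm or cause.
- Deaths: Section 14.4 includes unrelated deaths.
- Grade 3 or 4 events related to research participation, including assessments that Group 2 also undergoes: Section 14.4.
- Complications, and readmissions and deaths to 30 days after discharge: Sections 1.3.2, 9.3 and 10.4, compared between arms. The complications listed in Section 9.3 for abstraction are postoperative medical ones; falls and musculoskeletal injury are not named.
- Utilization and cost: Section 1.3.4 has three periods (admission to discharge, discharge to 2 months, 2 to 6 months), with visit indicators and diagnosis codes in Section 9.3. The pre-surgery exercise period is in none of them.
- Questionnaires: Section 14.4 says toxicities are collected this way from each subject, but the lists in Section 7 name no falls or injury instrument.

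**4. Length of the gap.** Section 8.4 expects a stay of 5 to 10 days. Adding 30 days puts the end of the readmission and death window at day 35 to 40 after surgery. Taking 6 months as about 180 days, 180 − 40 = 140 to 180 − 35 = 145 days of home exercise follow it, plus the weeks before surgery.

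**5. Why counts from the narrow rule cannot be read as harm.** Take 100 per arm (200 randomized 1:1) and a Group 2 count of 0 by construction. By Fisher's exact test, 6 against 0 is the smallest split with p < 0.05 (p = 0.029). Assume the same true event rate r in both arms and a share s of Group 1's events attributed to PEP. The Group 1 count is then binomial(100, r × s):

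| r (assumed) | s (assumed) | r × s | P(at least 6 against 0) |
|---|---|---|---|
| 10% | 25% | 2.5% | 4% |
| 10% | 50% | 5% | 38% |
| 20% | 50% | 10% | 94% |
| 30% | 50% | 15% | >99% |

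There is no true difference in any row.

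**6. What equal collection would buy.** For two proportions at two-sided 0.05, with p̄ the mean of p1 and p2, power = Φ{(|p1 − p2| − 1.96√[2p̄(1 − p̄)/n]) / √[(p1(1 − p1) + p2(1 − p2))/n]}. For 10% against 20% with n = 100: (0.10 − 1.96 × 0.0505)/0.05 ≈ 0.02, so power is 51%. All rates are assumed:

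| Group 2 vs Group 1 | 100 per arm | 75 per arm (25% dropout) |
|---|---|---|
| 5% vs 10% | 27% | 21% |
| 5% vs 15% | 66% | 53% |
| 5% vs 20% | 90% | 80% |
| 10% vs 20% | 51% | 40% |
| 10% vs 25% | 80% | 68% |

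**The case against.** The strongest reply is that the narrow sentence is only one side of an inconsistent section. The definition is cause-neutral, the questioning is open and not limited by arm, and the subset is said to include PEP-caused events, which need not mean that it contains nothing else. That is fair, and it is why the point is a contradiction to be resolved and not a settled rule that Group 2 events go unrecorded. But if the list is not exhaustive, nothing states what else belongs in it.

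A reader might infer that Group 2 can contribute no safety data at all, that a harm of home exercise could not be detected, or that the safety committee sees data from one arm only. The documents do not support this. The routes in step 3 reach both arms, and medically attended events in months 2 to 6 should appear in the utilization data, which depend neither on calls nor on attribution. Nor is it right to set a full series of weekly contacts in Group 1 against none in Group 2, since Group 2 has visits and recall contacts. It is also unclear whether the 30-day limit applies to complications or only to readmissions and deaths.

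Two qualifications remain. Section 14.4 makes seriousness one step in evaluating an event already detected, so serious event reporting partly inherits the ambiguity. And utilization is analysed as visits and cost, not as adverse events.

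Finally, limited collection is defensible in a low-risk study, and all-cause recording after lung resection brings in unrelated events. That is a real cost, and it argues for a short defined list.

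**Conclusion.** The point holds in this form. Section 14.4 contradicts itself on which events are recorded. Under its narrow rule Group 2 cannot enter the subset during comparative follow-up, and under its wide rule Group 1 is asked more often. The affected events are falls, injuries and other non-serious events, mainly before surgery and in about 140 to 145 days of home exercise after the 30-day window. For these, no symmetric capture and no table by arm is planned. The duration assumes a 180-day follow-up and the stated length of stay.

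The 94% in step 5 and the powers in step 6 rest on assumed rates and attribution shares and show scale only. They say that counts from the narrow rule cannot separate harm from attribution, and that equal collection would give an interpretable comparison able to detect only large differences. The primary 6MW analysis is not affected. This should be corrected, but it does not undermine the trial's main question.

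**What to change.** In Section 14.4:
- Replace the two rules with one, and remove the references to a study drug.
- Count events from randomization in both arms.
- Record injuries, falls and events needing medical attention regardless of cause, using the same question at the existing discharge, 2-month and 6-month visits. At the discharge visit the question should reach back to randomization, so that the pre-surgery period is covered.
- Assign relatedness after the event is recorded.
- Leave the IRB reporting list unchanged.

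In Section 10, add a descriptive table by arm. Events found only through Group 1 calls should be shown separately and kept out of the between-arm comparison.

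The cost is about one case report form page at visits that already take place, plus entering and following some unrelated post-surgical events. The follow-up rule in Section 14.4 makes that more than data entry alone, which is a reason to keep the list short. Recall at visits will miss some minor events, but in the same way in both arms.
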